7.6.4 Adverse Event Data Collection

The following data will be collected on an Adverse Event case report form for each adverse event experienced during the 30-day adverse event monitoring period:

- Event term
- Narrative description of event
- Start and stop date/time of event
- CTCAE grade
- Seriousness (yes/no) – *if yes, see further below*
- Relationship to protocol therapy
- Action taken with regard to protocol therapy (including therapy start and stop dates)
- Did AE cause subject's withdrawal from study (yes/no)?
- Outcome of treatment-related variable

In addition, the following variables will be collected for SAEs:

- Date AE met criteria for SAE
- Date Investigator became aware of serious AE

- Criteria met for “seriousness” (see Section 7.3)
- If hospitalization or prolongation of hospitalization:
 - Date of hospitalization (if applicable)
 - Date of discharge (if applicable)
- If death:
 - Date of death (if applicable)
 - Cause of death (if applicable)
 - Autopsy performed (yes/no) (if applicable)
- Description of SAE(s)

8.0 AGENT INFORMATION

8.1 Naloxegol

Please refer to Investigator’s Brochure for more comprehensive information. IDS will be responsible for all naloxegol storage, preparation, accountability, and dispensing throughout the trial.

Other names for the drug: MOVANTIK™

Mechanism of action (or Product description): Naloxegol is an antagonist of opioid binding at the mu-opioid receptor. At recommended dose levels, naloxegol functions as a PAMORA (Peripherally Acting Mu-Opioid Receptor Antagonist) in tissues such as the bowel, thereby decreasing the constipating effects of opioids. Naloxegol is a PEGylated derivative of naloxone, and a substrate for the P-gp. The presence of the PEG moiety in naloxegol reduces its passive permeability as compared with naloxone. Due to the reduced permeability and increased efflux of naloxegol across the blood-brain barrier, related to P-gp substrate properties, the central nervous system penetration of naloxegol is negligible at recommended dose levels, limiting the potential for interference with centrally mediated opioid analgesia.

Availability: provided by AstraZeneca, free of charge

How supplied: Study drug tablets are supplied as mauve, oval, biconvex, film coated, and intagliated with “nGL” on one side and “25” on the other.

Tablets will be supplied in 25-mg dose form, in high-density polyethylene (HDPE) bottles. IDS will dispense a 14-day supply of naloxegol at the initiation of the initial treatment phase for those patients randomized to Arm A. For patients randomized to Arm B, IDS will dispense a 14-day supply of naloxegol at the initiation of the crossover treatment phase. Patients who choose to participate in the optional extension portion of the study will receive a 28-day supply every 4 weeks during the extension phase.

Naloxegol will be packaged and labeled by AstraZeneca. It will be clearly marked according to national requirements regarding use for clinical trial investigation only and will be labeled with drug name, study reference number, and storage conditions.

Storage and stability: Naloxegol will be stored and locked in a secure location within IDS, with access restricted to pharmacy personnel only. All study drug will be stored in original containers until dispensed to study subjects. Naloxegol must be stored at room temperature between 20-25C (68-77F). Excursions are permitted to 15-30C (59-86F). Storage temperature will be

monitored

Preparation: Given its oral formulation, there is no product preparation required. IDS will prepare 14-day and 28-day supplies of naloxegol for dispensing to subjects according to randomization assignment and phase of study participation.

Route of administration for this study: Naloxegol will be administered as a single 25-mg tablet, once daily. Subjects will be instructed to take naloxegol on an empty stomach 1 hour before breakfast or 2 hours after their first meal of the day.

Side effects: The most common side effects associated with naloxegol are gastrointestinal in nature: abdominal pain, diarrhea, nausea, flatulence, vomiting, headache, and excessive sweating. Patients taking naloxegol may also experience additional symptoms of opioid withdrawal, including chills, anxiety, irritability, and yawning. There is also risk of developing abdominal or intestinal wall perforation.

8.1.1 Return and Retention of Study Drug

Remaining drug is to be destroyed on-site, according to UCSD Moores Cancer Center IDS drug destruction policy.

8.1.2 Drug Accountability/Subject Compliance

Records of study medications used, dosages administered, and intervals between visits will be kept during the study. Subjects will be asked to fill out a daily study drug diary while taking naloxegol and bring with them, along with any unused study drug, when they return to clinic every 14 days during the initial and crossover treatment phases, and at each in-person visit during the optional extension phase. A review of the subject-completed study drug diary and pill count will be performed by a member of the study team at each of these visits. In addition, a study team member will contact the patient weekly via telephone to perform pill counts if no in-person visit has occurred with the patient during a previous week.

Final drug accountability will be noted at the completion of the trial. Patients will be asked to return all unused medication at the end of the study.

9.0 STATISTICAL CONSIDERATIONS

9.1 Study Design/Study Endpoints

The proposed study is a prospective, single-center, feasibility trial. Ideally, a phase III placebo controlled trial would be completed to demonstrate the efficacy of naloxegol in cancer patients with OIC. However, placebo controlled trials are inherently difficult to accrue to in supportive oncology. Plus, the prior attempt at a phase III placebo controlled trial failed to accrue patients, and was closed early. We believe that a more feasible trial design would be a randomized phase II crossover study. The crossover design has multiple advantages including the potential for increased statistical efficiency requiring smaller sample sizes. Additionally, the crossover study design should appeal to patients more so than a classic placebo-controlled study because all patients will receive the experimental drug that has the potential to offer benefit. Additionally, patients will serve as their own controls, thus minimizing potential confounding factors. A brief washout period before crossover of 3 days based on the elimination half-life of 10 hours (5 half lives, ~50 hours) is also clinically appropriate and is not expected to impact cancer patient symptom management. Prior to embarking on a large phase III placebo controlled crossover study we propose to conduct a smaller simpler phase II crossover study to confirm feasibility of

the crossover strategy.

9.2 Sample Size and Accrual

The primary aim of this study is feasibility – specifically feasibility will be defined as completion of all study drugs over 4 weeks. For the primary aim we believe an acceptable completion rate would be at least 70%. Assuming a true completion rate of 85% (H_A), a sample size of 50 patients would have an 80% power to show that the true rate is at least 70% (H_0), using a one-sided exact test with $\alpha=0.05$. Any dropout or loss to follow up after the initiation of study treatment will be categorized as a non-completer and remain in the analytic sample. Thus we plan to recruit until 50 subjects have commenced study treatment.

The Palliative Care Service sees approximately 1,200 new inpatient consults and approximately 250 new outpatient cancer consults per year, and is integrated into the cancer care delivery model. OIC is a common symptom in patients with cancer-related pain and requires burdensome self-titration of laxatives for prophylaxis and treatment. Potential study participants will be recruited primarily from the outpatient clinic at Moores Cancer Center, where an estimated 70% of our patient population is currently being treated for OIC. We anticipate that enrollment will be completed in approximately 12 months, therefore, the expected accrual rate is approximately 5 patients per month.

Ethnic Category	Accrual Targets		
	Sex		
	Females	Males	Total
Hispanic or Latino	4	3	7
Not Hispanic or Latino	25	28	53
Ethnic Category: Total of all subjects	29	31	60
Racial Category			
American Indian or Alaskan Native	1	1	2
Asian	3	2	5
Black or African American	4	2	6
Native Hawaiian or other Pacific Islander	1	1	2
White	20	25	45
Racial Category: Total of all subjects	29	31	60

9.2.1 Evaluable Subjects and Subject Replacement

Analyses of secondary endpoints will be performed using data from patients that have both baseline and follow-up information.

We will characterize patients that drop out early by comparing baseline demographic data of the early dropouts to the patients who complete treatment. This will allow us to identify patients at risk of not completing treatment, which will provide critical information when defining eligibility criteria for future trials in this study population.

9.3 Data Analyses Plans

All analyses will be conducted using the latest version of R.

9.3.1 Primary Endpoint

The primary aim of this study is feasibility – specifically feasibility will be defined as completion

of all study procedures over the first 4 weeks of study treatment. For the primary aim we believe an acceptable completion rate would be $\geq 70\%$. We will assess this using a one-sided binomial exact test, where a p-value ≤ 0.05 will be considered statistically significant.

9.3.2 Safety Endpoint

Safety endpoints will be evaluated by monitoring AEs from clinical and laboratory reporting. Adverse events will be classified according to the NCI-CTCAE version 4.03. Trends in the distribution and severity of the AEs across the study groups will be assessed by examining the count of total AEs and count of AEs at each severity level over the course of the 2 weeks for the initial treatment and over the 2 weeks of the crossover treatment phases of the study.

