	
Safety endpoints will be evaluated by monitoring adverse events adverse events from clinical and laboratory reporting, using the NCI-CTCAE. Trends in the distribution and severity of adverse events across the study groups will be assessed by examining the count of total adverse events and count of adverse events at each severity level over the course of the 2 weeks for the initial treatment and over the 2 weeks of the crossover treatment phases of the study.
 
Secondary outcome measures are the effect of naloxegol versus usual care on; bowel movements per week, stool quality using the BSS,² occurrence and grade of adverse events using the NCI CTCAE version 4.03,³ health related quality of life utilizing the PAC-SYM⁴ & PAC-QOL,⁵ and changes in patient reported pain using the Brief Pain Inventory.⁶ For variables in the secondary aim, we plan to use generalized linear mixed effects models (GLM) to determine the impact of naloxegol on each endpoint over the course of 2 weeks for the initial treatment and crossover treatment phases of the study, achieved by treating the crossover arm as a time-dependent covariate. Within the GLM model; count of bowel movements per week will be assessed using a Poisson model. Stool quality (BSS, 7 point Likert-type scale), PAC-SYM (5 point Likert-scale), and PAC-QoL (5 point Likert-scale) will be assessed using an ordinal logistic model. The two parts of the BPI-sf (Intensity of pain and inference of pain) are calculated as the mean of several questions; as such they will be assessed as a continuous outcome with possible transformation for skewness if necessary. To control for the multiple comparisons a Bonferroni-Holm (e.g. Stepwise Bonferroni) method will be applied to the combined secondary and exploratory analyses, using an omnibus $\alpha = 0.05$.
 
Exploratory aims include laxative compliance (weekly pill counts), healthcare resource utilization (per electronic medical record evaluation of emergency room visits, hospitalizations, telephone encounters, and Mychart encounters), and patient preference (as evidenced by patient desire to continue naloxegol optional 12-week extension).
 
For analysis of differences in weekly pill counts between naloxegol and usual care, we plan to use a generalized linear mixed effects model to determine the impact of naloxegol on weekly pill counts, over the course of 2 weeks for the initial treatment and crossover treatment phases of the study, achieved by treating the arms as a time-dependent covariate. Within this model the weekly pill counts will be assessed using a Poisson model. Count of healthcare utilization resource, will be the sum of total utilizations (summed separately for each of the two weeks for initial treatment and cross over phase). Differences in healthcare utilization between the arms will be determined by fitting a Poisson regression model (or negative binomial in the case of over dispersion) of treatment arm on bi-weekly utilization count. We will examine patient preference by calculating a 95% confidence interval for the proportion of patients who wish to continue the optional 12-week extension.

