2.2 Secondary Objectives

1. To determine the frequency of naloxegol versus usual care on OIC as defined by ≤ 3 bowel movements per week.
2. To evaluate naloxegol versus usual care on stool quality using the Bristol Stool Scale (BSS).²
3. To describe the adverse events associated with naloxegol when administered daily in this patient population and to compare the adverse events associated with Naloxegol with adverse events observed with usual care, using the National Cancer Institute Common Terminology Criteria for Adverse Events (NCI CTCAE) version 4.03.³
4. To evaluate health related quality of life utilizing the Patient Assessment of Constipation Symptoms (PAC-SYM)⁴ and Patient Assessment of Constipation Quality of Life (PAC-QOL).⁵
5. To evaluate changes in patient reported pain using the Brief Pain Inventory-Short Form (BPI-sf).⁶

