2.4 Endpoints

The primary endpoint on this study is defined as completion of all study drug over the first 4 weeks of study treatment (initial and crossover treatment phases).

Secondary endpoints include number of bowel movements per week, as captured on the Patient bowel movement diary (**Appendix F**), stool quality as measured by the Bristol Stool Scale (**Appendix G**), safety defined as the rate of drug-related adverse events experienced assessed according to the NCI's CTCAE v4.03 toxicity criteria, and health related quality of life and pain measures as assessed by the PAC-SYM, PAC-QOL, and BPI-sf, within the first 4 weeks of study treatment (see **section 9.3.3**).

Exploratory endpoints will include drug administration compliance as measured by weekly pill counts by a member of the study team, healthcare resource utilization as defined by the number of number of emergency room visits, hospitalizations, telephone encounters, and EPIC mychart

encounters related to signs and symptoms of constipation, and patient preference (yes/no) for naloxegol to treat OIC as defined by choice of participation in the optional extension phase of the study.

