7.1 Adverse Event Monitoring

Adverse event data collection and reporting, which are required as part of every clinical trial, are done to ensure the safety of subjects enrolled in the studies as well as those who will enroll in future studies using similar agents. AEs are reported in a routine manner at scheduled times during a trial. Additionally, certain AEs must be reported in an expedited manner to allow for optimal monitoring of patient safety and care.

As far as possible, each adverse event should be evaluated to determine:

- duration (start and end dates)
- severity (grade)
- seriousness
- relationship to study agent
- action taken (i.e., none, study agent modification, medical intervention)
- outcome (i.e., resolved without sequelae, resolved with sequelae, ongoing)

AE monitoring begins at the time of informed consent signature and ends 28 days following the last administration of study treatment.

All patients experiencing an AE, regardless of its relationship to study drug will be monitored until:

- the event resolves or the symptoms or signs that constitute the event return to baseline;
- any clinically significant abnormal laboratory values have returned to baseline;
- there is a satisfactory explanation other than the study drug for the changes observed; or
- death.

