7.4 Relationship

The relationship to the IP of each AE/SAE will be evaluated by the investigator using the following levels:

- **Not related:** The temporal relationship of the clinical event to the administration of IP makes a causal relationship unlikely; and other drugs, therapeutic intervention or underlying conditions provide a sufficient explanation for the observed event.
- **Related:** The temporal relationship of the clinical event to the administration of the IP makes a causal relationship possible; and other drugs, therapeutic interventions or underlying conditions do not provide sufficient explanation for the observed event. A clear-cut temporal association with improvement on cessation of the study drug or recurrence upon rechallenge may also be observed.

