9.3.3 Secondary Endpoints

Secondary outcome measures are the effect of naloxegol versus usual care on; bowel movements per week, stool quality using the BSS,² occurrence and grade of AEs using the NCI CTCAE version 4.03,³ health related quality of life utilizing the PAC-SYM⁴ & PAC-QoL,⁵ and changes in patient reported pain using the BPI-sf.⁶

For variables in the secondary aim, we plan to use generalized linear mixed effects models to determine the impact of naloxegol on each endpoint over the course of 2 weeks for the initial treatment and crossover treatment phases of the study, achieved by including treatment group as a categorical covariate, and including a categorical time effect to account for a potential period effect. Counts of bowel movements per week will be assessed using a Poisson model. Stool quality (BSS, 7 point Likert-type scale), PAC-SYM (5 point Likert-scale), and PAC-QOL (5 point Likert-scale) will be assessed using an ordinal logistic model. The two parts of the BPI-sf (Intensity of pain and inference of pain) are calculated as the mean of several questions; as such they will be assessed as a continuous outcome with possible transformation for skewness if necessary.

To control for the multiple comparisons, a Bonferroni-Holm (e.g. Stepwise Bonferroni) method will be applied to the combined secondary and exploratory analyses, using an omnibus $\alpha = 0.05$.

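### The safety endpoint in Section 2.4 (drug-related AEs) has no matching analysis: Section 9 specifies only all-cause event totals and counts by grade, and uses neither relationship nor event term

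*Combined protocol and SAP*

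**What the plan says.** - **Section 2.4, Endpoints:** "safety defined as the rate of drug-related adverse events experienced", graded by CTCAE v4.03, within the first 4 weeks.
- **Section 2.2, objective 3:** describe the AEs seen with naloxegol and "to compare the adverse events associated with Naloxegol with adverse events observed with usual care".
- **Section 9.3.2:** trends in distribution and severity between the arms "will be assessed by examining the count of total AEs and count of AEs at each severity level over the course of the 2 weeks" of each treatment phase. The Statistical Methodology part of the Study Summary says the same: "examining the count of total adverse events and count of adverse events at each severity level".
- **Section 9.3.3:** the secondary outcomes include "occurrence and grade of AEs using the NCI CTCAE version 4.03". A general statement then assigns mixed models, with treatment and period terms, to the secondary variables. Model families are named for bowel movements, BSS, PAC-SYM, PAC-QOL and BPI-sf, but not for AEs.
- **Section 7.4:** "The relationship to the IP of each AE/SAE will be evaluated by the investigator", as related or not related.
- **Section 7.6.4:** the AE form records the event term and "Relationship to protocol therapy".
- **Section 6.1:** safety analyses cover everyone dosed at least once with study drug.

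**The concern.** The endpoint definition and the analysis describe different quantities. Section 2.4 asks for a rate restricted to drug-related events. Section 9.3.2 gives event counts with no restriction by relationship and no stated denominator of patients per treatment. Objective 3 needs to know which events occurred, and a total or a count per grade cannot show that.

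At stake is the safety information that this pilot passes on to the larger crossover trial for which Section 9.1 presents it as preparation. Section 4.5 allows anticancer therapy during the study, so an all-cause total may consist largely of events that have nothing to do with naloxegol. More nausea or more withdrawal-type symptoms on naloxegol could then go unseen in the planned output. If the tables by term and the handling of relatedness are chosen after the data are in, the choice can follow the results.

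**Working it through.** **1. The plan's own figure.** No power or precision is stated for safety. The only power figure is for the primary endpoint: N = 50, 70% versus 85%, one-sided exact test at 0.05. The rule is at least 41 completers of 50, with exact alpha 0.040 and power 0.791, which agrees with the stated 80%. Nothing below depends on it.

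**2. The texts side by side.**

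| Needed | Asked for in | Collected in | Analysed in Section 9? |
|---|---|---|---|
| Relationship to drug | 2.4 | 7.4, 7.6.4 | No |
| Type of event | 2.2, objective 3 | 7.6.4 | No |
| Rate (needs a denominator) | 2.4 | 6.1 gives an overall population | Counts only in 9.3.2 |
| Grade | 2.4 (CTCAE) | 7.2, 7.6.4 | Yes |
| Naloxegol versus usual care | 2.2, objective 3 | by phase and arm | Counts in 9.3.2; unspecified model in 9.3.3 |

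**3. Which named harms are reached by another planned comparison?** Section 8.1 lists 7 common side effects (abdominal pain, diarrhoea, nausea, flatulence, vomiting, headache, sweating) and 4 further withdrawal symptoms (chills, anxiety, irritability, yawning): 7 + 4 = 11, leaving perforation aside.
- Partly covered, 2: abdominal pain (PAC-SYM items 1-4) and diarrhoea (BSS type 7).
- Touched indirectly, 2: flatulence (the PAC-SYM bloating item) and irritability (PAC-QOL item 13, only as attributed to the patient's condition).
- Not covered: 11 - 2 - 2 = 7.

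**4. How a total hides one harm (illustration; all rates assumed).** Suppose one type of event occurs 1.0 times per patient on naloxegol and 0.5 on usual care, a true ratio of 2. Suppose other events occur b times per patient on both. The ratio of totals is (b + 1.0)/(b + 0.5): 1.50 at b = 0.5, 1.33 at b = 1, 1.20 at b = 2 and 1.11 at b = 4.

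**5. Denominators (25 per arm assumed).** At 85% completion, non-completers are 50 × 0.15 = 7.5, about 8.
- If 4 in each arm leave before Day 18, each treatment is taken by 25 + 21 = 46 patients. The ratio of raw counts at equal per-patient rates is 46/46 = 1.00.
- If all 8 are in Arm B and leave before Day 18, naloxegol is taken by 25 + 17 = 42 and usual care by 50. The ratio is 50/42 = 1.19.
- With equal dropout risk, the chance that all 8 fall in Arm B is C(25,8)/C(50,8) = 0.2%, even before requiring that they leave before Day 18. The 19% is an extreme bound.

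**6. Precision of the added tables (Clopper-Pearson 95% CI).** 0/50: 0-7.1%. 0/46: 0-7.7%. 0/42: 0-8.4%. 5/46: 3.6-23.6%. 10/46: 10.9-36.4%. This is enough to describe, not to confirm.

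**The case against.** **Section 9.3.3 already compares AEs.** A reader might infer from 9.3.2 that AEs get no model at all. The documents do not support that: 9.3.3 and the synopsis place occurrence and grade among the outcomes assigned to mixed models, and a patient-level model uses only the periods that a patient contributes. This stands. What is missing is the model family and any use of relationship or term.

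**CTCAE classification and the word distribution imply tables by term.** Such tables are not excluded. But 9.3.2 states how distribution will be assessed, and the method is total and per-grade counts.

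**Relatedness is already defined.** A reader might infer that drug-related has no fixed meaning, since 7.1 says "relationship to study agent", 7.4 refers to the IP and 7.6.4 to protocol therapy. That goes too far. Section 1.2 describes naloxegol as the study agent, usual care comes under Other Agents in 1.3, and Section 8 covers naloxegol alone, so 7.1 and 7.4 point to the same drug. Only the label in 7.6.4 is loose.

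**All-cause counts are the safer comparison.** The trial is open-label, so attribution is made knowing the treatment, and relatedness to naloxegol has no counterpart in Arm B's first period. This stands and shapes the fix.

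**Deleting the restriction to drug-related events in 2.4 would suffice.** It would remove the contradiction, but objective 3 would still have no description by type of event.

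**It is a feasibility pilot and the DSMB sees all AEs.** No planned decision rule uses these counts, which limits the weight of the point. The DSMB summary in Section 10.6 is monitoring and does not supply the endpoint.

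**Conclusion.** The point holds as a mismatch between endpoint and analysis. Section 2.4 defines a drug-related rate and objective 3 asks for description and comparison. Section 9 specifies all-cause totals and grade counts, plus an incompletely specified model of occurrence and grade. The defined endpoint would not be produced, although the data for it are collected.

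The effect on any AE comparison cannot be stated, because the documents give no AE rates. The tally of 7 uncovered harms in 11 shows how little the symptom scales fill the gap; those scales do not measure AE incidence in any case. A reader might take the 19% count distortion as expected, but it needs every non-completer to be in one arm and gone before crossover, and even dropout gives 0%. The primary feasibility endpoint is unaffected. The change should be made before analysis. It is not a reason to alter the design.

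**What to change.** **In 9.3.2 and the synopsis**
- Keep the total and per-grade counts as the all-cause comparison.
- Add, by treatment being taken at onset, the number and proportion of patients with at least one event, with 95% CI. Show these by CTCAE term and for the harms named in 8.1: GI events, withdrawal-type symptoms, headache and sweating.
- Use as denominator the patients who started that treatment, and clarify in 6.1 that this means naloxegol or usual care.
- List events starting in the Day 15-17 washout separately.
- Report naloxegol-related AEs, by the existing 7.4 definition, as a descriptive rate for naloxegol periods. This delivers the 2.4 endpoint.
- Base the naloxegol versus usual care comparison on all-cause events, because attribution is unblinded.

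**In 9.3.3**, state that these summaries are descriptive and outside the Holm family.

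**Leave 7.1 and 7.4 unchanged.** Redefining relationship as relationship to whatever treatment is being taken would disturb the causality wording behind SAE reporting, and the judgement would still be unblinded.

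**Cost:** wording changes in 6.1, 9.3.2, 9.3.3 and the synopsis, and a few extra tables from data already collected. Estimates will be imprecise at about 50 patients. Nausea, vomiting and abdominal pain have competing causes in patients on anticancer therapy, and the related-AE rate rests on open-label attribution.

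### Safety is summarised as raw adverse-event counts with no per-treatment denominator, although the endpoint is defined as a rate and comparison with usual care is an objective

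*Combined protocol and SAP*

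**What the plan says.** Section 9.3.2 looks at trends in adverse events (AEs) across the study groups by "examining the count of total AEs and count of AEs at each severity level", separately for the two weeks of initial treatment and the two weeks after crossover. The synopsis says the same. Neither gives a number of patients with an event, a number at risk or person-time.

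Four other places bear on this:

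- Section 2.4 lists as a secondary endpoint "safety defined as the rate of drug-related adverse events experienced". That is a rate, and it covers drug-related events only.
- Section 2.2, objective 3, sets out in part "to compare the adverse events associated with Naloxegol with adverse events observed with usual care".
- Section 6.1 restricts safety analyses to patients who took one or more doses of study drug, within the first four weeks. It does not turn this into a denominator for each treatment.
- Section 9.3.3 includes "occurrence and grade of AEs using the NCI CTCAE version 4.03" among the secondary outcomes and says "we plan to use generalized linear mixed effects models to determine the impact of naloxegol on each endpoint", with treatment and a categorical time effect for period. It then gives a model type for bowel movements, stool scale, PAC-SYM, PAC-QOL and BPI-sf, but none for AEs.

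**The concern.** The quantity in the safety section is not the endpoint in Section 2.4: a count is not a rate, and all events are not drug-related events.

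In a two-period crossover, a patient lost in period 1 contributes events to the first treatment and can contribute none to the second. If more patients leave the naloxegol-first sequence (Arm A) in period 1, fewer start usual care, and naloxegol shows more events for that reason alone. If more leave the usual-care-first sequence (Arm B), naloxegol looks safer than it is. Exposure can also fall without dropout, because Section 4.6 provides for holding naloxegol.

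A total also cannot tell many events in one patient from one event in each of many patients. AE data are collected daily (Section 4.1), and gastrointestinal symptoms can recur.

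What is at stake is how the AE comparison reads, which is a stated objective. The primary completion endpoint is not involved.

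**Working it through.** **Step 1: the plan's own figure.** Section 9.2 gives N = 50, 70% under the null, 85% under the alternative, a one-sided exact test at 0.05 and 80% power. The smallest passing number of completers is 41 of 50: exact alpha 0.040, power 0.791. The normal approximation gives 0.805. The stated 80% is reproduced, and nothing below changes it. A trial that just passes has 50 − 41 = 9 non-completers, which is used here as a scale for dropout.

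**Step 2: numbers starting each treatment.** Allocation is 1:1 (Section 10.3); 25 per sequence is assumed. Let dA and dB be the patients leaving Arm A and Arm B in period 1.

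- Naloxegol starters = 25 + (25 − dB) = 50 − dB
- Usual-care starters = 25 + (25 − dA) = 50 − dA

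With equal AE risk per starter on both treatments, the expected pooled count ratio is (50 − dB)/(50 − dA), and the true ratio is 1.00.

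**Step 3: leaving midway.** Suppose instead that leavers contribute 7 of the 14 days of period 1, with an equal AE rate per day.

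- Naloxegol days = 14(25 − dA) + 7dA + 14(25 − dB)
- Usual-care days = 14(25 − dB) + 7dB + 14(25 − dA)

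| Period-1 leavers, Arm A / Arm B | Count ratio, equal risk per starter | Count ratio, leaving midway |
|---|---|---|
| 4/4 | 46/46 = 1.00 | 616/616 = 1.00 |
| 4/5 | 45/46 = 0.98 | 602/609 = 0.99 |
| 7/2 | 48/43 = 1.12 | 623/588 = 1.06 |
| 9/0 | 50/41 = 1.22 | 637/574 = 1.11 |
| 0/9 | 41/50 = 0.82 | 574/637 = 0.90 |
| 8/0 (about 15% dropout) | 50/42 = 1.19 | 644/588 = 1.10 |
| 15/0 (30% dropout) | 50/35 = 1.43 | 595/490 = 1.21 |

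Dividing by starters (first column) or by patient-days (second column) returns 1.00 in every row, because the true risks or rates were set equal. The documents give no dropout split, so every unbalanced row is an assumption.

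**Step 4: by phase.** The table pools both periods, whereas Section 9.3.2 looks at each phase. For the 7/2 split under equal risk per starter, phase 1 compares 25 with 25 starters (ratio 1.00). Phase 2 compares 25 − 2 = 23 naloxegol starters with 25 − 7 = 18 usual-care starters: 23/18 = 1.28. Viewing phases separately moves the imbalance into phase 2; it does not remove it.

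**Step 5: repeated events.** With 50 starters, ten events in one patient and one event in each of ten patients both give a total of 10. The percentage of patients affected is 1/50 = 2% in the first case and 10/50 = 20% in the second.

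**The case against.** The strongest reply is that the plan does more than count. Section 9.3.3 places occurrence and grade of AEs under mixed models with treatment and period, which could handle repeated events within a patient. Section 6.1 names a safety population. Section 9.3.2 is descriptive, and a count table can carry its Ns. The trial is a small feasibility study with completion as its primary endpoint.

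Much of this stands. A reader might infer that AEs have no planned model at all; Section 9.3.3 does not support that. But AEs are the one secondary outcome there without a distribution, unit or offset, so an analyst could not reproduce a single intended AE analysis. The Section 6.1 population is not specific to a treatment: a patient lost in period 1 belongs to it without ever having started the second treatment.

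It is also fair that the figures lean towards an unfavourable case. Non-completion is wider than period-1 dropout. A patient who misses doses or procedures, or who leaves in period 2, has still started both treatments. Early leaving from naloxegol also cuts naloxegol exposure, which is why the midway column is about half as far from 1.00.

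A reader might further infer an inflated false-positive rate. In a simulation with 50 patient-periods per treatment and a mean of 1 AE per patient-period, testing totals as independent events raised a nominal 5% to about 11%, 17% and 25% for between-patient variance of 0.5, 1 and 2. Those means and variances are assumptions, and the two periods were drawn independently. If the same patients have many events in both periods, the inflation shrinks. Above all, Section 9.3.2 states no test of totals, so the documents do not support this as a defect of the plan.

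**Conclusion.** The point holds in a limited form. The safety section plans raw counts with no per-treatment denominator, while the endpoint is a rate of drug-related events and the objective is comparative. The model sentence that might fill the gap is not specified for AEs.

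The distortion is conditional. With 9 of 50 patients leaving in period 1 and equal risk per starter, the pooled ratio runs from 0.82 to 1.22 at the extreme splits, or 0.90 to 1.11 if they leave midway. It is 1.00 when dropout is balanced. A reader might conclude that the comparison is biased, or biased against naloxegol. The documents support neither, because they give no dropout split and the direction depends on which sequence loses patients. The loss of information about repeated events needs no dropout.

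This is a cheap improvement, not a threat to the trial's main conclusion.

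**What to change.** Amend Sections 9.3.2 and 9.3.3 and the synopsis as follows:

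1. For each treatment and period, report the number and percentage of patients with at least one AE (overall, by worst grade, and drug-related) among patients who started that treatment in that period. Add AEs per patient-day on treatment.
2. Specify the AE model that Section 9.3.3 already implies: either a mixed logistic model for any AE with treatment and period, or a mixed count model with treatment, period and a log-exposure offset. State whether this comparison belongs to the Holm family in that section.
3. Keep raw counts as supporting description.
4. Reconcile the drug-related events of Section 2.4 with the total events of Section 9.3.2, and say what drug-related means while a patient is on usual care. Section 7.4 judges relationship to the IP, and Section 7.6.4 records it for protocol therapy.
5. State which treatment, if either, is assigned events arising in the Day 15–17 washout.

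The cost is a few sentences and a little programming. AE start and stop dates and therapy start and stop dates are already collected (Section 7.6.4). Sample size and the primary analysis do not change.
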